1.2 Study objectives and endpoints

1.2.1 Primary objective

Demonstrate that ofatumumab 20 mg sc once every 4 weeks (q4w) is superior to teriflunomide 14 mg po once daily in reducing the frequency of confirmed relapses as evaluated by the ARR in patients with relapsing MS.

1.2.2 Key secondary objectives

All disability related key secondary objectives will be addressed in the combined data (meta-analysis) from this study and the second study of identical design. All other objectives will be addressed based on the data from this study alone.

The key secondary objectives are to evaluate if ofatumumab 20 mg sc q4w is superior to teriflunomide 14 mg po once daily on the following efficacy measures:

1. Time to disability worsening as measured by 3-month confirmed worsening (3mCDW) on The Expanded Disability Status Scale (EDSS)
2. Time to disability worsening as measured by 6-month confirmed disability worsening (6mCDW) on EDSS
3. Time to disability improvement as measured by 6-month confirmed improvement (6mCDI) on EDSS
4. Number of T1 Gd-enhancing lesions per MRI scan
5. Number of new or enlarging T2 lesion on MRI per year (annualized T2 lesion rate)

6. Neurofilament light chain (NfL) concentration in serum
7. Rate of brain volume loss (BVL) based on assessments of percentage brain volume change from baseline

1.2.3 Other secondary objectives

Evaluate if ofatumumab 20 mg sc q4w is superior to teriflunomide 14 mg po once daily on the following efficacy measures:

[figure not shown]
- Time to first relapse
- Annualized relapse rates > 8 weeks after the onset of treatment
- Risk of a 3mCDW > 8 weeks after the onset of treatment
- Risk of a 6mCDW > 8 weeks after the onset of treatment
- Time to a 6-month confirmed cognitive decline (6mCCD), defined as a 4-point worsening on Symbol Digit Modalities Test (SDMT)
- Time to 6mCDW or 6mCCD, whichever is reached first
- Change in cognitive performance relative to baseline as measured by the SDMT
- Time to 6-month confirmed worsening of at least 20% in the timed 25-foot walk test (T25FW)
- Time to 6-month confirmed worsening of at least 20% in the 9-hole peg test (9HPT)
- Time to 6mCDI sustained until the EOS as measured by EDSS
- Number of new or enlarging T2 lesions between Month 12 and EOS
- Change in T2 lesion volume relative to baseline
- Proportion of patients with no evidence of disease activity (NEDA-4; defined in [Section 2.7.1](#)) at year 1 and 2
- Physical and psychological impact of MS disease as measured by the MSIS-29

In the subgroup of newly diagnosed, treatment-naïve patients, evaluate if:

- High NfL (above median) concentration at baseline is predictive of higher disease activity post baseline
- Patients with a high NfL (above median) concentration at baseline benefit from a stronger relative treatment effect of ofatumumab vs teriflunomide
- The safety profile of ofatumumab vs teriflunomide is comparable in patients with high NfL (above median) concentration at baseline

Evaluate the safety and tolerability of ofatumumab 20 mg sc q4w compared to teriflunomide 14 mg po once daily

Evaluate the pharmacokinetics (PK) of ofatumumab

2 Statistical methods

2.1 Data analysis general information

Novartis statistical and programming team will be performing the CSR analysis as planned in this document unless otherwise specified. The Statistical Analysis System (SAS) 9.4 and/or R 15.2.1 or higher versions will be used.

Statistical safety analyses for the independent Data Monitoring Committee (DMC) will be conducted by a CRO. The process is described in the DMC charter.

Unless otherwise stated, summary tables/figures/listings will be on all patients in the respective analysis sets. Categorical data will be presented as frequencies and percentages. For continuous data, mean, standard deviations, median, 25th and 75th percentiles (optional), minimum and maximum will be presented.

The registration CSR analysis cut-off date will depend on the EOS date. All data up to this date will be included in the registration CSR. A complete analysis of the post-treatment safety follow-up will be provided in the final CSR when all patients have completed Safety FU epoch.

For efficacy analyses on the full-analysis set (FAS), all available data until the end of treatment epoch date (i.e., excluding the data collected in the safety follow-up epoch) will be considered and no other cut-offs will be applied.

For efficacy analyses on the per-protocol set (PPS), only on-treatment (as defined in [Section 2.1.1](#)) data will be considered, that is, for patients randomized to receive ofatumumab, data obtained 30 days after the last injection date will be excluded from the analyses; for patients

randomized to receive teriflunomide, data obtained after the last dose date of randomized study medication will be excluded from the analyses.

For safety analyses on the safety set, only data up to and including the safety cutoff of 100 days (5 x 20 days takes the long half-life of the comparator-drug into account) after last administration of study drug will be considered. Therefore, observations obtained more than 100 days after last administration of study drug will be excluded from the analyses. Nevertheless, all serious adverse events (SAE) and all deaths, regardless of the safety cut-off will be summarized.

Statistical models will include adjustments for regions by pooling centers to regions. The definition of region is intended to correspond to that used for the stratification of the randomization (as defined in [Section 5.8](#)). However, the definition of region may be modified if that is indicated based on statistical criteria (e.g., non-convergence). For statistical analysis where region is adjusted in the statistical models, regions “Asia Pacific” and “Latin America” will be combined with region “Other” due to small number of patients in these 2 regions.

Presentation of p-values: p-values from statistical tests will be presented with 3 decimal places, or as <.001 where applicable. Statistically significant p-values will be flagged with an asterisk. In general, this is when p-values ≤ 0.05 . For key-secondary disability-related hypotheses, two asterisks will be used if p-value ≤ 0.04875 ($=2*[0.025-0.025*0.025]$) as these hypotheses will be tested at alpha minus alpha-squared (this condition will be footnoted on the relevant outputs).

All data (collected or derived) will be listed appropriately.

2.1.1 General definitions

Below summarize some general definitions to be used in the rest of the document.

Table 2-1 **general definitions**

Study treatment/Study drug	Both the investigational drug (ofatumumab) and the active comparator (teriflunomide) will be referred as study treatment or study drug.
Actual treatment	Actual treatment patients received. Ideally, actual treatment should be the same as randomized treatment. It could be different in case study drug is mis-dispensed. If patients received both investigational drug and active comparator accidentally during the study, their actual treatment will be the treatment to which they were exposed longer in duration. For safety analysis, patients will be analyzed according to the actual treatment received.
Date of first administration of study drug/first dose date	The first dose date of active study drug administration. For determining this date, matching placebo dummy treatment records will be excluded.
Date of last administration of study drug/last dose date	The last dose date of active study drug administration. For determining this date, matching placebo dummy treatment records will be excluded.

Study Day 1 or Day 1	The date of first administration of study drug/first dose date.
Study Day	All other study days will be labeled relative to Day 1. For events with dates on or after Day 1, study day for the event is calculated as (event start date – first dose date + 1). For events with dates before Day 1, study day for the event is calculated as (event start date – first dose date). Day 0 will not be used.
Duration of an event	Duration of an event is calculated as (event end date – event start date +1).
1 month	30 days; to be used in defining 3-month or 6-month confirmed disability worsening or improvement.
4 weeks	28 days; to be used in determining target days of scheduled visits. It is based on the scheduled injection frequency for ofatumumab (during the maintenance phase).
Day post-study drug discontinuation	Day post-study drug discontinuation for a particular event is calculated as (event start date – study drug discontinuation date).
Baseline	Baseline is the last assessment obtained prior to the first administration of study drug. No visit windows will be needed for the identification of baseline assessment. For pulse and blood pressure vital sign values, the baseline is the average of the non-missing values of the 3 measurements taken on the last visit prior to the first administration of study drug. The pre-injection assessment values on Day 1 vital sign CRF page will not be used for baseline derivations.
On-treatment period	For patients randomized to receive ofatumumab, on-treatment period includes days from the first injection date until 30 days after the last injection date; for patients randomized to receive teriflunomide, on-treatment period includes days from the first dose date until the last dose date. This definition considers patients on ofatumumab are scheduled to inject every 28 +/- 3 days. The on-treatment definition applies to efficacy analyses only. For calculation of compliance to study drug administration, similar definition of on-treatment period except based on actual treatment assignment will be used.
Safety cutoff (off-treatment)	Safety cutoff: Unless explicitly otherwise stated (e.g. SAEs and deaths), data up to and including the safety cutoff of 100 days after permanent study drug discontinuation will be

	included in the analysis and data beyond this time point for a given patient will be excluded from the safety analysis. The safety cutoff of 100 days (5x20 days) takes the long half-life of both investigational and comparator-drug into account. The safety cutoff applies to safety analyses only.
Nominal visits	Nominal visits are defined as all scheduled visits as per the clinical study protocol including the EOS and EOT visits. The definition of nominal visit excludes unscheduled visits. Only vital signs data collected on Day 1, Day 7, Day 14 and Month 1 protocol scheduled visit and ECG data collected on EOT and EOS visits will be summarized by nominal visit.
End of Study (EOS)	EOS, used in the context of individual patients, refers to EOS visit. EOS, used in the context of the entire study, refers to completion of treatment epoch for all patients.
End of Treatment (EOT)	EOT refers to EOT visit. Only patients who prematurely discontinue study drug but agree to continue to follow the schedule of assessments in the treatment epoch will have EOT visit.
End of treatment epoch date	This date is the date of discontinuation/study phase completion as recorded in the Study Phase Completion CRF page.
Last assessment on drug	It is the last assessment with non-missing value taken before or on the date of last administration of study drug. No visit windows will be needed for the identification of the last assessment on drug evaluation.

Table 2-2 Definition of time in key analyses

Time in study (ARR)	Time in study for ARR will be calculated as (end of treatment epoch date – first dose date+1)/365.25. The time in study by patient will be used as an offset variable to adjust for the various length patients have been observed and at risk of a confirmed MS relapse in the study.
Time from screening scan (MRI: key secondary analysis related)	T2 lesions: The time from screening scan will be calculated as (date of last scheduled MRI scan with a non-missing value for the number of new or enlarging T2 lesions during the treatment epoch – date of screening scan +1)/365.25. Brain volume change: Time of MRI assessment from screening scan will be calculated as (date of the scheduled MRI scan – date the screening scan +1)/365.25.

Time at risk for AE	Time at risk for AE is defined as the number of days spent in the study, from first to last administration of study drug, plus the safety data cut-off of 100 days. Time at risk for AE will be used for tables reporting AEs (including both SAE and non-SAE). If the corresponding last day of time at risk for AE is after the analysis cut-off date, then it will be truncated by the analysis cut-off date as defined in Section 2.1 .
Time at risk for SAE	Time at risk for SAE is defined as the number of days spent in the study from the day of first administration of study drug to the end of study date (including safety follow up epoch). Time at risk for SAE will be used only for tables reporting SAEs. If a patient is still in safety follow up epoch at the time of reporting, time at risk for SAE is the number of days from the day of first administration of study drug to the analysis cut-off date as defined in Section 2.1 .

2.1.2 Visit windows

2.1.2.1 Visit windows for treatment epoch

Visit-windows will be used for both efficacy and safety data summaries by visit. Visit windows define a time period “around” the targeted visit date as defined in the evaluation schedule of the clinical study protocol. Visit-windows are non-overlapping, and defined without gaps between consecutive visit windows. The width of visit windows may vary over the course of the study period.

Baseline assessments are defined in [Section 2.1.1](#) and do not require a visit window.

The purpose of visit windows is to analyze data based on the actual study days (rather than "nominal" visits). E.g., if a patient’s Month 1 visit is delayed; it is possible that the Month 1 data be re-aligned to visit-window Month 2 and be summarized under Month 2.

- For **efficacy analyses** (including PK concentration by visit analysis) all nominal visits (i.e. excluding unscheduled visits) will be mapped into one of the defined visit-windows. Note: for the derivation of disability worsening or improvement all visits (scheduled and unscheduled) need to be considered before the worsening or improvement can be confirmed (see [Section 2.6.1.1](#)). Similarly, for No Evidence of Disease Activity (NEDA-4), all visits (scheduled and unscheduled) need to be considered ([Section 2.7.1](#)).

-For **safety analyses** all visits (scheduled and unscheduled) will be mapped to visit windows. Safety data from unscheduled visits may be reported separately if applicable.

It is possible that more than one assessment of a patient fall into a particular visit-window. [Section 2.1.2.3](#) deals with the statistical approaches to handle multiple visits in a given visit-window.

Tables displaying summary statistics “by visit” will also use the term *visit-window* as column header; this is to remind the reviewer that multiple assessments of a patient might be summarized. Below tables provide visit-windows definitions for applicable parameters.

Table 2-3 Visit-windows for EDSS*/T25FW

Visit-window	Start day	Target Day	End day
Week 12	1	84	126
Week 24	127	168	210
Week 36	211	252	294
Week 48	295	336	378
Week 60	379	420	462
Week 72	463	504	546
Week 84	547	588	630
Week 96	631	672	714
Week 108	715	756	798
Week 120	799	840	881

* For EDSS, assessment on Day 1 will be excluded as baseline EDSS can occur on Day 1 per protocol.

Table 2-4 Visit-windows for 9HPT/SDMT/MSIS-29/

Visit-window	Start day	Target Day	End day
Week 24	1	168	252
Week 48	253	336	420
Week 72	421	504	588
Week 96	589	672	756
Week 120	757	840	923

Table 2-5 Visit-windows for MRI/

Visit-window	Start day	Target Day	End day
Week 48	1	336	504
Week 96	505	672	839

Table 2-6 Visit-windows for routine laboratory values

Visit-window	Start day	Target Day	End day
Week 4	1	28	56
Week 12	57	84	126
Week 24	127	168	210
Week 36	211	252	294
Week 48	295	336	378
Week 60	379	420	462
Week 72	463	504	546

Week 84	547	588	630
Week 96	631	672	714
Week 108	715	756	798
Week 120	799	840	881

Table 2-7 Visit-windows for vital signs*

Visit-window	Start day	Target Day	End day
Week 12	1	84	126
Week 24	127	168	210
Week 36	211	252	294
Week 48	295	336	378
Week 60	379	420	462
Week 72	463	504	546
Week 84	547	588	630
Week 96	631	672	714
Week 108	715	756	798
Week 120	799	840	881

*Data collected from Day 1, Day 7, Day 14 and Month 1 protocol scheduled visit will not be mapped to the visit windows due to different data collection on those visits.

Table 2-8 Visit-windows for B-cell counts

Visit-window	Start day	Target Day	End day
Week 1	1	7	10
Week 2	11	14	21
Week 4	22	28	56
Week 12	57	84	126
Week 24	127	168	210
Week 36	211	252	294
Week 48	295	336	378
Week 60	379	420	462
Week 72	463	504	546
Week 84	547	588	630
Week 96	631	672	714
Week 108	715	756	798
Week 120	799	840	881

Table 2-9 Visit-windows for ADA data

Visit-window	Start day	Target Day	End day
Week 4	1	28	98
Week 24	99	168	252

Week 48	253	336	504
Week 96	505	672	839

Table 2-10 Visit-windows for biomarker data

Visit-window	Start day	Target Day	End day
Week 12	1	84	210
Week 48	211	336	504
Week 96	505	672	839

Table 2-11 Visit-windows for PK data

Visit-window	Start day	Target Day	End day
Week 4	1	28	56
Week 12	57	84	126
Week 24	127	168	252
Week 48	253	336	504
Week 96	505	672	839

2.1.2.2 Visit windows after study drug discontinuation

For summaries of data collected after study drug discontinuation, data from both treatment epoch and safety follow-up epoch will be considered. All reporting will be done based on visit windows defined relative to the last administration of study drug.

The visit window definitions are provided in [Table 2-12](#) where the Start day and End day are relative to the date of last administration of study drug. For the “Last assessment on drug”, the last assessment with non-missing value taken before or on the date of last administration of study drug will be summarized (no visit window applies). For the “Week 12 after LDD” visit-window, assessments taken at least 1 day after but no more than 126 days after the date of last administration of study drug will be considered. LDD stands for last dose date and will be footnoted in applicable outputs.

Table 2-12 Visit-windows after study drug discontinuation

Visit-window	Start day	Target Day	End day
Last assessment on drug	NA	NA	NA (see above or section 2.1.1)
Week 12 after LDD	2	84	126
Week 24 after LDD	127	168	210
Week 36 after LDD	211	252	294
Week 48 after LDD	295	336	378
Week 60 after LDD	379	420	462

Week 72 after LDD	463	504	546
Week 84 after LDD	547	588	630
Week 96 after LDD	631	672	714
Week 108 after LDD	715	756	798
Week 120 after LDD	799	840	881

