2.8.3.4 Other special lab results

Other non-routine laboratory data include pregnancy test results, B-cell counts, teriflunomide plasma levels, total IgG, total IgM, [REDACTED]. All data will be listed appropriately.

The B-cell counts, total IgG, total IgM, neurofilaments [REDACTED] will be summarized using descriptive statistics by treatment group and visit-window.

In addition, number and percentage of patients with B-cells < the lower limit of normal (LLN) value (i.e., B-cell depleted) will be presented by treatment group and visit-window. Graphic presentation of B-cell counts distribution will also be provided by treatment group and visit-window. All B-cell summaries defined in this section will include data up to the end of the on-treatment period (i.e., last dose date + 30). This is to provide more accurate information about B-cell depletion because fast B-cell repletion is expected after study drug discontinuation and applying the safety cutoff (i.e., last dose date +100) would mix repletion and depletion to some degree.

Number and percentage of patients meeting the notable low level criteria in IgG or IgM at least once will be provided by treatment group. A notably low IgG level is defined as a level that is 20% below the LLN and a notably low IgM level is defined as a level 10% below the LLN.

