2.8.7 Safety evaluation during the Safety follow-up

Safety data collected after last administration of study drug includes adverse events, vital signs, routine laboratory parameters, laboratory assessments to measure total IgG, total IgM, B-cell repletion and residual teriflunomide PK levels, and eCSSRS. No safety cutoff date will be applied in the analyses defined in this section. Safety data within the safety cutoff date but after last administration of study drug will also be included.

The number and percentage of patients with at least one TEAEs that started after the date of last administration of study drug will be reported by SOC, preferred term, and treatment group. The subset of patients in SAF who had data reported after the date of last administration of study drug will be included in the analysis and the number of patients in this subset will be the denominator in calculating the percentage.

The vital signs data collected after study drug discontinuation will be summarized as summary statistics of the vital sign measures and of the change from baseline in the vital sign measures by treatment group for each visit-window after study drug discontinuation (as defined in [Section 2.1.2.2](#)). The SAF will be used for these analyses.

The B-cell counts and its change from baseline values will be summarized by treatment group for each visit-window after study drug discontinuation. In addition, the change from last assessment on study drug in B-cell count will also be summarized similarly. Graphic presentation of B-cell counts distribution will also be provided by treatment group for each visit-window after study drug discontinuation. Additionally, number and percentage of patients with B-cells within 10%, 10 to 20%, 20 to 50%, 50% to 80%, 80 to 100% of baseline, or with B-cells < the lower limit of normal (LLN), or with B-cell repletion will be presented by treatment group for each visit-window after study drug discontinuation. B-cell repletion is defined as B-cell counts having returned to their baseline value or to LLN (i.e., $\geq 100\%$ of baseline or $\geq \text{LLN}$). The analysis will be limited to the subset of patients in SAF who had B-cell count data after the date of last administration of study drug; the number of patients in this subset will be the denominator in calculating the percentage.

Patients with teriflunomide plasma data will be listed as only small percentage of patients are expected to have such data.

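### SAP 2.8.7 counts ofatumumab patients still within their dosing interval as not repleted, because its B-cell table has no off-drug requirement and a fixed denominator

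*SAP*

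**What the plan says.** **Clock.** SAP 2.1.1 defines the last dose date (LDD) as "The last dose date of active study drug administration" and adds: "For determining this date, matching placebo dummy treatment records will be excluded". For an ofatumumab patient, LDD is therefore the last injection, even if capsules continue.

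**Windows.** SAP 2.1.2.2 and Table 2-12 count from LDD. The Week 12 window takes "assessments taken at least 1 day after but no more than 126 days after the date of last administration of study drug".

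**Repletion table.** SAP 2.8.7 gives, by arm and window, the number and percentage of patients in bands of baseline B-cell count, below the lower limit of normal, or repleted. The analysis is "limited to the subset of patients in SAF who had B-cell count data after the date of last administration of study drug", and "the number of patients in this subset will be the denominator in calculating the percentage".

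**Depletion tables.** SAP 2.1.1 states: "For patients randomized to receive ofatumumab, on-treatment period includes days from the first injection date until 30 days after the last injection date". SAP 2.8.3.4 ends its B-cell summaries at LDD + 30 days, because "applying the safety cutoff (i.e., last dose date +100) would mix repletion and depletion to some degree".

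**Schedule.** Protocol Table 6-1 has a B-cell sample at EOS and no dispensing of study drug there. Protocol 5.5.4 sets injections 28 ± 3 days apart. Under protocol 3.1, patients who complete on drug may be eligible for an open-label ofatumumab extension. Those who do not enter it go into the Safety Follow-up.

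**The concern.** The table is meant to show how B-cells recover once ofatumumab stops, but its entry rule asks only for a count dated after the last injection. A completer's EOS sample usually meets that rule while the patient is still within the normal dosing interval. A patient who then enters the extension has not stopped ofatumumab, gives no off-drug sample in this study, and still sits in the denominator as not repleted.

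The SAP treats the same sample in two ways. In 2.8.3.4 it is on-treatment evidence of depletion. In 2.8.7 it is post-discontinuation evidence of non-repletion. The reason 2.8.3.4 gives for its upper limit applies equally to a lower limit in 2.8.7, which has none.

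At stake is the trial's own description of repletion. Protocol 3.3 predicts from Phase 2 modelling that about 5 months are needed for 80% repletion and that the vast majority of patients replete within 9 months. A reader would compare the 2.8.7 percentages with those predictions.

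**Working it through.** **1. The plan's window limits reproduce.** Targets are 84 days apart, and midpoints give the ends: (84 + 168)/2 = 126, (168 + 252)/2 = 210, and so on to 798, as in Table 2-12. The last end would be 840 + 42 = 882, against 881 printed, which is immaterial.

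**2. Overlap with the on-treatment period.** LDD + 1 to LDD + 30 is 30 of the 126 days in the Week 12 window (24%). Starting at LDD + 31 would leave 126 − 31 + 1 = 96 days.

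**3. Does the start day distort the values of patients who are followed?** Hardly. SAP 2.1.2.3 selects the quantitative assessment closest to day 84. Assume the EOS sample is equally likely on any of days 1 to 31 after LDD and the Month 3 follow-up sample comes 84 ± 14 days later. The EOS sample is chosen only if the later one falls beyond day 126. That needs EOS day + visit deviation ≥ 43, which holds for 3 + 2 + 1 = 6 of 31 × 29 = 899 combinations, or 0.7%. A simulation of 200,000 draws gave 0.6%. For early discontinuers who stay on the 84-day schedule, a simulation on the same assumptions chose a sample at or before day 30 in 1.2%. If repletion yes/no were handled as a qualitative variable, the worst-record rule would pick the early depleted sample instead. The SAP does not say which rule applies.

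**4. Effect of the denominator.** Let p be the true repleted proportion among patients followed off drug, and e the share of the subset whose only sample after LDD is an EOS sample within the dosing interval. Assume those EOS samples are not repleted and everyone else has a value in the window. Then:

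reported proportion = p × (1 − e)

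For example, take 100 patients in the subset, 25 with only the EOS sample and 75 followed. If 80% of the 75 have repleted, that is 60 patients, and the table shows 60/100 = 60%.

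| p | e = 0 | e = 10% | e = 25% | e = 50% |
|---|---|---|---|---|
| 80% | 80% | 72% | 60% | 40% |
| 50% | 50% | 45% | 37.5% | 25% |
| 20% | 20% | 18% | 15% | 10% |

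The values of p are illustrative. As 2.8.7 is worded, the factor (1 − e) applies in every window.

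**5. Who makes up e.** Extension entrants belong to it in both reports. SAP 2.1 ties the registration report's cut-off to the EOS date, and 2.8.7 says that report holds only partial follow-up data. Completers who will be followed but have no follow-up sample yet therefore also belong to e at that point. Extension uptake is not stated in either document.

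**6. Per-window reading.** If the denominator were the patients with a value in that window, EOS-only patients would appear in Week 12 alone. The formula would then apply there, with e as their share of the Week 12 values. Later windows would be largely unaffected.

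**The case against.** Several objections have force.

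- **Cause.** A reader might infer that the Table 2-12 start day is the main fault. Step 3 shows otherwise: for patients who are followed, the closest-to-target rule avoids the early sample about 99% of the time. The population and denominator rule in 2.8.7 drives the bias. Count summaries after Week 12 are not affected, and neither is the number of patients repleted in those windows.
- **Size.** With a high assumed extension uptake the understatement becomes several-fold: e = 80% turns 80% into 16%. The documents do not support any such figure. Protocol 3.1 says only that completers may be eligible, and at e = 0 the bias vanishes.
- **Other tables.** It is tempting to extend the point to adverse events, vital signs and eCSSRS. SAP 2.8.7 declares that data after LDD but inside the 100-day safety cut-off are also included there, and no adverse event is lost from the main tables. SAP 2.1.1 confines the on-treatment definition to efficacy, with a similar one for compliance, and 2.8.3.4 extends it only to B-cells. Moving the start for other safety data would be a preference.
- **Consequence.** A reader might think the 9-month follow-up or the washout advice depends on this table. Both rest on Phase 2 modelling, and an individual's follow-up beyond 9 months depends on that patient's own central laboratory results. No hypothesis test uses the table.

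None of this answers the core point. Declaring an overlap does not make a patient who continues ofatumumab a valid member of a post-discontinuation denominator.

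**Conclusion.** The point holds for the B-cell table in SAP 2.8.7. Followed as written, it understates ofatumumab repletion by the factor (1 − e) in every window. The direction is certain whenever any patient's only count after LDD is an EOS sample within the dosing interval, which a planned extension and a registration cut-off tied to EOS make likely. The size is not known, because e is not in the documents. For p = 80% the result runs from 80% at e = 0 to 60% at e = 25% and 40% at e = 50%. Under per-window denominators the bias shrinks to the Week 12 window for the most part.

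These figures assume that EOS-only samples are not repleted and that all other patients have a value in the window. The defect affects one descriptive safety table. The primary and key secondary analyses are untouched.

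**What to change.** For the B-cell tables in SAP 2.8.7 only:

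- use ofatumumab samples taken after the on-treatment period, that is, later than last injection + 30 days, to match 2.8.3.4;
- include only patients with at least one such sample;
- in each window, use as denominator the patients with a value in that window, and print that number;
- state whether repletion status follows the closest-to-target or the worst-record rule.

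The lower limit for teriflunomide should be stated too. SAP 2.1.1 ends that arm's on-treatment period at the last dose, while 2.8.3.4 writes LDD + 30 without naming an arm.

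The cost is SAP wording and a programming change. Samples from days 1 to 30 after the last injection leave this table, but they already appear in the 2.8.3.4 tables. SAP section 1 provides for a registration report and a final report after the final database lock, so the change can still serve the complete follow-up analysis.
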